Length of hospital stay will be recorded for all patients following the surgical procedure with the day after surgery defined as postoperative day one. The medical record will be reviewed following discharge to determine if hospital discharge date was dependent on POUR or other reason (e.g. uncontrollable pain, mobility requiring physical therapy or inpatient rehabilitation, or other medical complications delaying discharge).

In addition to the primary and secondary outcome measures, baseline characteristics will be collected on all patients via the medical record including age, height and weight, past history of postoperative urinary retention or diagnosis of benign prostatic hyperplasia (not on treatment), length and type of surgery, estimated blood loss during surgery, total intravenous fluids administered perioperatively, time to oral analgesic use (in hours), total analgesic use during the postoperative period, time to first postoperative mobility (in hours), and any adverse events thought to be related to administration of the study medication. These variables will be used as baseline comparisons between the two groups to ensure homogeny and be used in statistical adjustment if differences between the groups are significant after randomization.

Unanticipated events:

There is the potential for patients to experience urinary retention as outpatients after inpatient urinary retention has resolved. This is quite unusual to occur after urinary retention has resolved as defined above and may indicate the patient needs further investigation by a urologic surgeon. Patients will be counseled by nursing staff prior to dismissal regarding the signs and symptoms of urinary retention and directed to seek medical attention with appropriate urology referral should the treating physician deem this is appropriate.

Patients experiencing prolonged postoperative urinary retention (> 5 days) will be seen by the urology consult service for recommendations regarding further investigation and treatment. The study group designation may be broken at this point to determine which group the patient is in regarding treatment medication if deemed necessary by the urology consult service to guide further treatment.

Patients experiencing severe adverse events such as profound hypotension, arrhythmia, or allergic reaction will be evaluated by the primary neurosurgical team with appropriate intervention or consultation as deemed necessary.

Quality Control:

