Patients experiencing possible severe side effects from this medication will be instructed to contact the primary neurosurgical team prior to hospitalization. During hospitalization, any patients experiencing such effects will be immediately evaluated by the neurosurgical team with appropriate intervention or consultation as deemed necessary. The PI or Co-PI will be informed of any serious adverse events thought to be related to medication administration and appropriate steps will be taken to determine whether the adverse event was related to the medication under investigation or other patient medication/condition (e.g. narcotic analgesics, other cardiovascular medication, or dehydration). The decision to stop the study medication will be determined by the primary neurosurgical team responsible for the patient in collaboration with the PI/Co-PI after the seriousness of the event is taken into consideration. All serious adverse events will be reported to the Mayo IRB within 24 hours of the event taking place, and to the FDA if necessary. All major and minor adverse effects of the study medication (tamsulosin or placebo) will be recorded in the medical record and used for data analysis.

Inclusion of Women, Minorities, and Children:

Women will be included in this study. Minorities will be included in the study in the same proportion as they present to the outpatient neurosurgery clinic. Mentally disabled patients, prisoners, and children will be excluded from the study.

References:

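### Adverse events are collected and analysed only when thought to be drug-related, so the comparison between arms can miss or dilute an excess of hypotension, dizziness or arrhythmia

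*Combined protocol and SAP*

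**What the plan says.** Three places in the combined protocol and SAP govern adverse-event data.

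- **Outcome Measures, list of additional variables.** The last item is "any adverse events thought to be related to administration of the study medication". It follows age, weight, blood loss, fluids and analgesic use, in a list introduced as baseline characteristics. The next sentence gives the use of the whole list: "These variables will be used as baseline comparisons between the two groups to ensure homogeny", with statistical adjustment if the groups differ.
- **Adverse Events, analysis sentence.** "All major and minor adverse effects of the study medication (tamsulosin or placebo) will be recorded in the medical record", and these are to be used for data analysis.
- **Adverse Events, notification.** "The PI or Co-PI will be informed of any serious adverse events thought to be related to medication administration". In the same sentence, "appropriate steps will be taken to determine whether the adverse event was related to the medication under investigation or other patient medication/condition", with examples of the alternatives: "narcotic analgesics, other cardiovascular medication, or dehydration". Two sentences later, with no condition on cause: "All serious adverse events will be reported to the Mayo IRB within 24 hours of the event taking place".

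The Adverse Events section also names postural or orthostatic hypotension as the primary risk, at 0.2% on the 0.4 mg daily dose. It says blood pressure, heart rate and rhythm are monitored in all patients under existing ward procedures. The Analysis of the Data section does not mention adverse events.

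**The concern.** Whether a given patient's low blood pressure on the day after spine surgery comes from the study drug is seldom knowable at the bedside, least of all by staff blinded to the arm. Randomisation answers the question for the group, but only if events are counted before anyone judges their cause. The plan applies the judgement first and keeps what passes. The rival explanations that the protocol names are ordinary after this surgery, so events caused by the drug may be filtered out with the background.

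The Background says that no study of the newer uroselective drugs in postoperative patients has been reported. This trial's own comparison is therefore the main information that it can add on tolerability in this setting. Listing adverse events among variables used to check balance and adjust makes matters worse: they occur after randomisation and may be consequences of treatment, so they belong with the outcomes.

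**Working it through.** **1. Does any text lift the filter?** I set every place that touches adverse events side by side.

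| Place | What it covers | Relatedness condition? |
|---|---|---|
| Outcome Measures, additional variables | Data collected | Yes |
| Adverse Events, analysis sentence | Data analysed | Yes: all severities, but effects of the study medication |
| Adverse Events, notice to PI/Co-PI | Serious events | Yes |
| Adverse Events, report to IRB | Serious events | No |
| Adverse Events, ward monitoring | Vital signs in all patients | No, but clinical care and not a study variable |
| Quality Control, staff briefing | Emphasis on reporting adverse events | No, but sets no collection rule |
| Unanticipated events | Evaluation of profound hypotension, arrhythmia, allergic reaction | Patient care, not data collection |

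Nothing makes hypotension a study variable or plans an all-cause comparison by arm.

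**2. What could the filter cost?** The plan states no figure for this, so there is none to reproduce. The following is an illustration.

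*Inputs.* n = 175 per arm (Analysis of the Data). All-cause event rates of p_C = 15% on placebo and p_T = 25% on tamsulosin are assumptions, not in the documents. So are the shares attributed to study drug: b for background events and d for drug-caused events, each the same in both arms because attribution is blinded.

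*Formulas.* Counted rate on placebo = b × p_C. Counted rate on tamsulosin = b × p_C + d × (p_T − p_C). Expected count = 175 × rate. Power is exact binomial for the pooled z-test, two-sided 0.05.

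| b | d | Counted rates | Expected events | Power |
|---|---|---|---|---|
| 100% | 100% | 15% vs 25% | 26 vs 44 | 65% |
| 50% | 50% | 7.5% vs 12.5% | 13 vs 22 | 34% |
| 20% | 20% | 3% vs 5% | 5 vs 9 | about 15% |
| 10% | 10% | 1.5% vs 2.5% | 2.6 vs 4.4 | 9% |
| 10% | 30% | 1.5% vs 4.5% | 2.6 vs 7.9 | 37% |
| 20% | 50% | 3% vs 8% | 5 vs 14 | 54% |
| 10% | 50% | 1.5% vs 6.5% | 2.6 vs 11.4 | 70% |

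Example, last row: 0.10 × 0.15 = 0.015; 0.015 + 0.50 × 0.10 = 0.065.

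Where b = d, attribution has no discriminating value, and power falls steeply. Where staff recognise drug-caused events much better than background ones, the filter removes noise, and power can match or exceed that of counting everything.

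Other assumed rates with b = d behave in the same way. For 10% vs 20%, power is 76% with all events, 43% at 50% attribution, 18% at 20% and 11% at 10%. For 5% vs 10% it is 43%, 23%, 11% and 4%.

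**3. The protocol's own rate.** At 0.2%, 175 treated patients give 175 × 0.002 = 0.35 expected events, and the chance of at least one is 1 − 0.998^175 = 30%.

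**4. The two rules for serious events.** One has the PI or Co-PI told of serious events thought related. The other sends all serious events to the IRB within 24 hours. Both can be followed at once. What is missing is who files the IRB report, and how the study learns of a serious event that ward staff judge unrelated.

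**The case against.** **Ward records may already hold the data.** Vital signs are monitored in everyone, and Quality Control says most data come from the electronic record. This stands as far as it goes: all-cause hypotension may be recoverable. But the plan does not say it will be extracted or compared, and recoverability mainly shows that the change is cheap.

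**The analysis sentence may be broader than it looks.** It mentions placebo, which could suggest any event on study treatment. That reading is possible. Still, it speaks of effects of the medication, and the variable list in Outcome Measures carries an explicit relatedness condition.

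**Staff are briefed to report adverse events, and an operations manual is promised.** True, and the manual may widen collection. It is not among the documents, and the protocol does not say that it does.

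**The power loss depends on the assumptions.** This stands. A reader might infer from the rows with b = d that the filter destroys the safety comparison. The 10%/50% row, at 70% against 65%, shows that it need not. The assumed 10-point excess is also 50 times the protocol's 0.2% figure; at that rate the trial would say little with or without the filter.

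**The rules on serious events do not conflict.** This also stands. A reader might infer that the related-only notice contradicts or overrides the duty to report all serious events to the IRB. Nothing says that the IRB report must pass through that notice, or that the investigators may not be told of other events.

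**Conclusion.** The point holds in a limited form. Adverse events are filtered by presumed cause at collection and again at analysis, no text removes the filter, and no all-cause comparison by arm is planned. Drug-caused events can therefore be lost when staff blame another cause. If attribution is truly blinded, the loss should be similar in both arms and shrink the absolute difference without reversing it.

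The size is not determinable from the documents. Under assumed rates of 15% and 25%, filtered power spans about 9% to 70%, against 65% unfiltered. The documents support saying that the comparison can miss an excess, not that it will.

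A reader might also take the statement that benefits outweigh risks as a trial conclusion that uncounted events would protect. In the Adverse Events section it is a justification given before the trial, resting on earlier alpha-blocker studies and on what is known of tamsulosin.

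On serious events, the finding is an unstated route for those judged unrelated, not a contradiction. Overall this is a cheap improvement that should be made, and it casts no doubt on the primary efficacy analysis.

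**What to change.** 1. In Outcome Measures, drop the relatedness condition. Collect every serious adverse event, and at least hypotension or orthostasis, dizziness and arrhythmia, whatever the presumed cause, from existing ward monitoring and the electronic record. Define each event in advance so that extraction is the same in both arms.
2. Record the judgement of relatedness, made while blinded, as a separate descriptive field.
3. Move adverse events out of the baseline list. In Analysis of the Data, state that all-cause events will be compared by arm as a safety outcome, and are not candidates for covariate adjustment.
4. Reword the analysis sentence under Adverse Events to match.
5. Reconcile the two sentences on serious events: state how the PI or Co-PI learns of every serious event, including those judged unrelated, and who files the IRB report.

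The cost is a few more extracted fields and some redrafting. The downside is more background events in the safety tables, which the separate relatedness field helps a reader to interpret.

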*The following drugs are strong inhibitors of CYP3A4: ketoconazole, itraconazole, clarithromycin, ritonavir, indinavir/ritonavir, lopinavir/ritonavir, and conivaptan.⁴⁸

Randomization:

A consecutive sample of subjects that meet eligibility requirements and give informed consent will be randomized to two study groups via a randomization number generated from a random numbers table. Based on their randomization number patients will be given a prescription (for either tamsulosin or a likeappearing placebo) from the Mayo pharmacy at least one week prior to the date of surgery. The pharmacy will record which group the patient has been assigned to in a central pharmacy database. This database will then be used in the perioperative and postoperative period to maintain the patient's drug designation and administration while in the hospital. The randomization will be blinded to both the treating physician's team and the patient until the end of the study and data analysis is undertaken.

Drug Administration:

In order to achieve full steady state concentrations of the drug by the time of surgery, patients will be instructed to take the assigned drug for 5 days prior to surgery, as well as the morning of surgery. Thus, patients will be given 6 pills of the study medication or the like-appearing placebo at a preoperative clinic visit. On the morning of surgery patients will be admitted to Saint Marys Hospital as morning admissions and proceed to surgery that day based on the surgical schedule. Data on medication compliance will be collected and recorded at that time. Patients will continue taking tamsulosin 0.4mg or like-appearing placebo provided by the Mayo Pharmacy beginning on post-operative day one and continuing every day during their postoperative hospital course until the time of discharge. At that time the primary treating team will write an order to discontinue the study medication. Because each patient will be at therapeutic steady state concentrations of the drug by the time of surgery, shorter hospital stays should not underestimate the potential treatment benefit of this medication. Standard postoperative orders for patients undergoing decompressive cervical or lumbar laminectomy and/or spinal fusion have been in place for neurosurgical patients and will continue to be used during this study (postoperative order set

MC1156-404). The cost of the study medication will be covered by the study and patients will not be charged.

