An operations manual will be prepared prior to initiation of the study and will be distributed as necessary to all staff involved. Treating neurosurgeons and their respective physician extenders will be instructed on the study goals, risks, and expected outcomes, as well as the identification and recruitment of eligible patients to the study, including obtaining consent. Residents and staff neurosurgeons responsible for inpatients following surgery will be informed of the study goals and methodology with special emphasis on reporting adverse events and the appropriate means to resolution in conjunction with the principal investigator (PI)/co-principal investigator (Co-PI) and co-investigators prior to the study starting. Any questions or concerns arising in relation to the study will be forwarded to the primary investigator as these concerns arise.

Nursing staff responsible for patients in the postoperative period will continue to use the standard postoperative order sets for surgical patients undergoing spine procedures as well as the urinary retention protocol. An informational meeting will be arranged with the head nurses of the neurosurgical wards where postoperative patients will reside following surgery to discuss the goals, rationale, and methods particular to the study. Contact information for reporting adverse events or questions regarding study implementation will be provided before the study begins.

Any and all questions will be forwarded to the PI/Co-PI, or study co-investigators should the PI/Co-PI be unavailable, in a timely manner with multiple sources of contact available (i.e. pager, telephone numbers, e-mail addresses).

The Mayo Clinic Pharmacy will provide both the study drug (tamsulosin) and a like-appearing placebo. A labeling system to track patient assignments, but that blinds study subjects and investigators, will be utilized.

Data will be collected prospectively in an ongoing fashion for the duration of the study by investigators blinded to patient treatment group. Because the vast

majority of data will be collected from the EMR in a prospective fashion while the patient is either in the hospital or shortly thereafter, it is not anticipated that there will be much missing data.

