Studies using nonspecific alpha-1-adrenergic receptor blockade have shown benefit in reducing POUR with minimal adverse effects.^{12,13,30-37,39} Tamsulosin is regarded as being safer with respect to cardiovascular side effects than earlier generation alpha-1-antagonists due to its uroselective nature.^{45,49,50} The potential benefit of reduced incidence and duration of POUR, reduced morbidity associated with repeat intermittent catheterizations, reduced incidence of UTI, and reduced hospital length of stay outweigh the risks associated with administration of this medication.

The primary risk to human subjects taking tamsulosin in this study is postural or orthostatic hypotension, estimated to occur in 0.2% of patients taking the 0.4 mg daily dose of the drug. All patients will be regularly monitored with respect to blood pressure, heart rate, and rhythm according to existing standard postoperative procedures in place on the neurosurgical wards. Per the postoperative neurosurgery protocol, all patients are ambulated with the assistance of nursing staff until they are deemed safe for independent ambulation. Abnormal ejaculation was reported in 8.4% of patients taking the 0.4 mg daily dose. This risk should be minimal in the study given the short duration of time taking the study medication and decreased likelihood of sexual activity in the immediate postoperative period. There have been some reports of intraoperative floppy iris syndrome during cataract surgery during the short time they are on the study medication. Allergic type reactions have been reported rarely. Patients will be informed as to the signs and symptoms of

allergic reactions. Priapism has also been reported as a rare risk (less than 1 in 50,000). Male patients will be informed about the seriousness of this condition.

Other adverse reactions include headache, dizziness, rhinitis, infection, asthenia, back pain, diarrhea, pharyngitis, chest pain, cough increased, somnolence, nausea, sinusitis, insomnia, libido decreased, tooth disorder, and blurred vision. Postmarketing experiences have also shown infrequent reports of dyspnea, palpitations, hypotension, atrial fibrillation, arrhythmia, tachycardia, skin desquamation including reports of Stevens-Johnson syndrome, constipation, and vomiting. All risks are taken directly from the official FDA drug information sheet.¹⁶

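### Non-serious intraoperative hypotension need be recorded only if staff attribute it to study drug, although patients are operated on at intended steady state

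*Combined protocol and SAP*

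**What the plan says.** **Exposure.** Under Drug Administration, patients are to "take the assigned drug for 5 days prior to surgery, as well as the morning of surgery", with the stated aim of steady state by the time of surgery. The Background puts peak concentration at 4-8 hours after a fasting dose, so the morning dose can peak during the operation.

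**Operative data.** Outcome Measures lists variables to be taken from the medical record. Those from the operation include its length and type, "estimated blood loss during surgery, total intravenous fluids administered perioperatively". Intraoperative blood pressure, hypotension and vasopressor use are not named there or elsewhere. The same paragraph says that the listed variables serve for baseline comparison and for statistical adjustment where the groups differ.

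**Adverse events.** There are three rules:
- Outcome Measures collects "any adverse events thought to be related to administration of the study medication".
- The Adverse Events section says "All major and minor adverse effects of the study medication (tamsulosin or placebo) will be recorded in the medical record" and that these will be used in the analysis.
- For serious events the same section says "All serious adverse events will be reported to the Mayo IRB within 24 hours of the event taking place". This rule carries no condition on relatedness.

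**Monitoring.** Adverse Events states: "The primary risk to human subjects taking tamsulosin in this study is postural or orthostatic hypotension", put at 0.2%. Blood pressure, heart rate and rhythm are monitored "according to existing standard postoperative procedures in place on the neurosurgical wards". Under Unanticipated events, profound hypotension leads to clinical evaluation. It is not made a data item.

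**Briefing.** Quality Control describes an operations manual that "will be distributed as necessary to all staff involved". It directs its adverse-event emphasis to residents and staff neurosurgeons caring for inpatients after surgery. Anaesthesia staff are not named.

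**The concern.** Low blood pressure under anaesthesia has ready explanations other than study drug: the anaesthetic, blood loss, fluid balance. If recording depends on staff thinking of the drug, many non-serious episodes could go unrecorded in both arms. A randomised comparison does not need anyone to attribute single events. It needs complete counts in each arm, and the difference between arms then does the attribution.

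What is at stake is one safety comparison. The Significance section foresees routine perioperative use if the trial succeeds, and a surgeon or anaesthetist considering that would want to know whether the treated arm needed more pressure support during surgery. Under the plan as written, that comparison would rest on whatever staff happened to attribute to the drug.

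**Working it through.** **Step 1. Follow one event through the rules.** Take a fall in pressure during surgery, treated with a vasopressor, not serious, and judged by blinded staff to be due to anaesthesia.

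| Route | Does it require the event to be recorded? |
|---|---|
| Serious-event reporting to the IRB | No, the event is not serious |
| Adverse-event item in Outcome Measures | No, it is not thought related |
| Major and minor effects in Adverse Events | Not on the plain reading, which covers effects of study medication |
| Ward blood pressure monitoring | No, it is postoperative |
| Named operative variables | No; blood loss and fluids are at most indirect proxies |

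No route requires it. The gap is confirmed by reading and needs no arithmetic.

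**Step 2. The plan's own figures.** The planned size of 175 per arm (one-sided, 10% against 20% retention) is close to the 177 given by the pooled-variance formula with continuity correction. It is used below only as the number of patients. The only hypotension rate in the plan is the 0.2%, or 175 × 0.002 = 0.35 expected patients in the treated arm. That rate is postural and says nothing about pressure under anaesthesia, so there is no plan figure from which to derive the loss.

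**Step 3. Illustration on assumed rates.** Assumed, not in the documents: true intraoperative hypotension of 20% on placebo and 20% or 30% on tamsulosin, with a fraction f of episodes recorded. The fraction is taken as equal in both arms because staff are blinded. The recorded rates are f × p.

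- Risk difference: f(p_T − p_P), with SE = √[fp_T(1 − fp_T)/175 + fp_P(1 − fp_P)/175].
- Risk ratio: p_T/p_P, since f cancels, with SE of the log = √[(1 − fp_T)/(175fp_T) + (1 − fp_P)/(175fp_P)].
- 95% limits: ±1.96 SE.

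For 30% against 20% with f = 1, SE = √(0.30 × 0.70/175 + 0.20 × 0.80/175) = 0.0460, so the difference is 10.0 ± 9.0 points. With f = 0.25 the recorded rates are 7.5% and 5%, SE = √(0.075 × 0.925/175 + 0.05 × 0.95/175) = 0.0258, and the difference is 2.5 ± 5.1 points.

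| True rates, placebo v tamsulosin | f | Risk difference, points (95% CI) | Risk ratio (95% CI) |
|---|---|---|---|
| 20% v 30% | 1 | 10.0 (1.0 to 19.0) | 1.50 (1.03 to 2.18) |
| 20% v 30% | 0.5 | 5.0 (-1.9 to 11.9) | 1.50 (0.85 to 2.65) |
| 20% v 30% | 0.25 | 2.5 (-2.6 to 7.6) | 1.50 (0.65 to 3.44) |
| 20% v 30% | 0.10 | 1.0 (-2.3 to 4.3) | 1.50 (0.39 to 5.71) |
| 20% v 20% | 1 | 0.0 (-8.4 to 8.4) | 1.00 (0.66 to 1.52) |
| 20% v 20% | 0.25 | 0.0 (-4.6 to 4.6) | 1.00 (0.40 to 2.49) |

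Equal under-recording leaves the risk ratio unbiased but less precise, and shrinks the absolute difference by the factor f. With no true excess there is no bias on either scale. The narrower absolute interval in the last row describes recorded episodes, not all episodes.

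**The case against.** **No intraoperative hazard is established.** The named risk is postural, and the plan meets it with ward monitoring and assisted ambulation. The Background gives tamsulosin lower affinity for the vascular receptor subtype. This stands. A reader might infer that the trial would miss a known drug harm, but the documents do not support that: they allow for little or no excess.

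**The size is all assumption.** This also stands. The shrinkage at f = 0.25 follows directly from multiplying by 0.25, and it would mislead only if attributed reports were presented as the incidence of hypotension. The plan does not propose that.

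**The recording rules may be broader than they look.** Naming placebo in the minor-effects rule could be read as covering any event on study medication. Neurosurgeons are briefed on reporting, severe events during the hospital stay are evaluated at once, and the data lists in Experimental Design and Outcome Measures are open-ended. All of this permits recording. None of it requires recording of an unattributed, non-serious episode.

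**The data are probably in the chart.** This is a fair inference, although the documents do not say so. It makes the fix cheap. It does not replace naming the item, and any threshold, before the data are seen.

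**Adding fields beside blood loss and fluids could do harm.** Variables on that list may be used for adjustment, and a pressure difference caused by the drug would then be adjusted for as if it were a baseline imbalance. This objection is right, and the fix is written to avoid it.

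**Conclusion.** The point holds as a low-severity gap in safety data collection. Patients are deliberately on drug during anaesthesia, no intraoperative pressure or vasopressor item is named, and non-serious events are recorded only on attribution. A by-arm comparison of non-serious intraoperative hypotension would be incomplete.

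The actual loss cannot be derived from the documents. The illustration rests on an assumed placebo rate, an assumed excess and an assumed recording fraction equal in both arms. On those terms it shows the direction only: loss of precision always, and a diluted absolute difference if there is a true excess.

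Two stronger readings should be resisted. One is that serious hypotension could go unreported; serious events go to the IRB whatever their cause. The other is that the efficacy results are compromised; urinary retention, its duration and length of stay do not depend on this item.

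**What to change.** For every patient, regardless of attribution, abstract two items from the existing medical record: the lowest intraoperative blood pressure (or minutes below a threshold set in advance) and any vasopressor use. Report both by arm with 95% confidence intervals as descriptive safety outcomes.

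List them explicitly as post-randomisation safety outcomes, and keep them out of the Outcome Measures list of variables used for baseline comparison and adjustment. Naming the anaesthesia team in the Quality Control briefing would be a useful optional addition.

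The cost is slightly more chart abstraction. Sample size and randomisation do not change and, with the fields kept off the adjustment list, neither does the primary analysis.
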